3. Background (briefly describe pre-clinical and clinical data, current experience with procedures, drug or device, and any other relevant information to justify the research)

Preliminary Data:

We will apply rtfMRI-NF imagery training to people with cerebellar ataxia (CA), a movement disorder that results from progressive cerebellar degeneration. CA individuals experience poor balance, difficulty walking, severe hand tremors, abnormal eye movements, and slurred speech. A key function of the cerebellum is to orchestrate the fine timing and sequencing of motor functions [3]. The cerebellum recognizes spatial and temporal relationships for feedforward predictions [4-7] and then compares the predicted versus actual outcomes and adjusts its output to the cortex [6, 8, 9]. CA signs, therefore, fundamentally reflect a disruption in timing ability. Without a known cure, current treatments include palliative pharmacology and physical, occupational, and speech therapies to strengthen muscles and counteract the symptoms of disease progression [10]. While these treatments can slow the rate of motor loss, they focus on physical manifestations and do not target the underlying neural mechanisms involved, thereby missing the

root cause. Moreover, not all treatments are equally effective for each patient due to the heterogeneity of symptom presentations. We hypothesize that if patients could learn to "exercise" their own motor brain networks directly, they could optimize their rehabilitation.

The National Ataxia Foundation released a report in January 2021 describing the three symptoms that mattered most to those with CA: lack of balance, impaired mobility, and *decreased fine motor skills in the hand*. Uncoordinated hand movements make it difficult to perform activities of daily living, such as writing, typing, eating, drinking, holding a razor or toothbrush, etc. Fine motor skills, therefore, represent an important target for therapeutic intervention and can reasonably be tested in laboratory and MRI settings.

We compared performance of CA participants (N=17) and healthy controls (N=17) matched for age, sex, and education levels on a task that involved finger tapping in time with a visual cue that flashed at 1, 2, 3, and 4 Hz (Figure 1). Performance feedback was provided as a

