Exclusion criteria: History of Axis I psychiatric disorders (including alcohol and drug dependence), severe or unstable medical disorder, non-ataxia related neurological disorders, such as stroke or epilepsy, history of head injury that resulted in a loss of consciousness greater than 5 minutes and/or neurological sequelae, any condition that is contraindicated for the MRI environment (e.g., metal in the body, pacemaker, claustrophobia), or currently pregnant, and clinical diagnosis of multiple system atrophy (MSA, due to the disruption of the central autonomic network) or Friedrich's ataxia (FA, due to extensive involvement of the spinal cord and loss of sensory fibers in the peripheral nerves). MSA and FA differ substantially from other forms of CA and would greatly complicate interpretation of the data. Eligible subjects may be asked to refrain from medications that affect the central nervous system that would also make data difficult to interpret (e.g., sedatives) for an appropriate period of time prior to scanning. Participants will be excluded if they do not have a home computer with internet available to complete the 3-week at-home component of the study protocol.

6. Drugs/ Substances/ Devices

- a. The rationale for choosing the drug and dose or for choosing the device to be used.
- N/A
- b. Justification and safety information if FDA approved drugs will be administered for non-FDA approved indications or if doses or routes of administration or participant populations are changed.
- N/A
- c. Justification and safety information if non-FDA approved drugs without an IND will be administered.

N/A

7. Study Statistics

a. Primary outcome variable.

1) Overt tapping accuracy improvements will be analyzed by comparing the mean accuracy on overt tapping between baseline and final measures (pre- and post- NF) to compute a delta

measure that will indicate magnitude of accuracy improvement at each frequency (1 and 4 Hz). This will be analyzed using paired t-tests within frequency conditions.

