In our first study, the behavioral RSME deficits exhibited by cerebellar ataxia participants while performing the same overt tapping task as proposed in Aim 1 was quite robust at both 1 Hz and 4 Hz conditions (relative to controls, N=17 per group) [1]. Applying these data to our model revealed that a **sample size of at least 12** participants per group yielded at least 82% power at the .05 level, one-tailed, to reject the null hypothesis of no differences between groups, based on an effect size of at least .79 (large). Although the proposed study will not include healthy

controls, at least 12 CA participants should be sufficient to elicit RSME performance impairments.

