In our second study, a functional MRI study of CA participants and healthy controls while performing the same overt tapping task as proposed in Aim 1 revealed several brain regions that differed between groups at the 1 Hz and 4 Hz conditions (N=6 controls, N=10 ataxia): notably, right M1 and right cerebellar lobe V. Contrast values (1 Hz tapping – rest) for these regions were computed, using atlas-based boundaries [41, 42] for CA participants and healthy controls separately and entered into analyses. For the M1 region of interest (ROI), a sample size of at least 13 participants per group yielded 82% power at the .05 level, two-tailed, to reject the null hypothesis of no difference between groups at the 1 Hz condition, based on an effect size of 1.2 (large). For cerebellar lobe V, a sample size of at least 9 participants per group yielded 83% power at the .05 level, two-tailed, to reject the null hypothesis of no difference between groups. Similarly, strong between-group differences were revealed at the 4 Hz condition for the M1 ROI. Atlas-based contrast values (4 Hz tapping – rest) for M1 were computed for each group and entered into analyses. A sample size of at least 8 participants per group yielded 84% power at the .05 level, two-tailed, to reject the null hypothesis of no difference between groups at the 4 Hz condition, based on an effect size of 1.6 (large). However, group differences for cerebellar lobe V, not were significant in our fMRI study at the 4 Hz condition because the CA group was able to recruit this region vigorously in this tapping condition. Given the low number of participants per group in the functional MRI pilot study, additional brain ROIs were identified by trending between-group differences and entered into the model: left premotor cortex and bilateral lobes VIIB. For these ROIs, a sample size of 19-29 participants per group yielded at least 80% power at the .05 level, two-tailed, to reject the null hypothesis of no group differences, based on an effect size of at least .78 (large). These measures are conservative given that the ROIs were atlas-based rather than task-based (i.e., the ROI boundaries included voxels that did not differ between groups). Thus, a sample size of 29 would be expected to reveal neural activation abnormalities in a number of regions within the cortex and cerebellum in CA participants.

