In our third study, rtfMRI-NF was applied to healthy adults (N=17) while performing the overt tapping and imagery tasks proposed in Aim 1. Results revealed that several brain regions engaged during motor imagery positively correlated with RSME improvements: bilateral M1, right premotor cortex and the SMA. Atlas-based contrast values (motor imagery – rest) for these ROIs were computed. Entering into the model the correlation value and standard deviations between the mean contrast values per ROI and mean RSME "delta" revealed that **a** sample size of 17 - 22 participants yielded at least 81% power at the .05 level, one-tailed, to reject the null hypothesis of no linear relationship between motor imagery activation and RSME improvements.

Taken together, we propose to enroll N=30 CA participants into this study. This N will be overpowered for some aspects of the study, such as tapping accuracy. However, we are also taking into consideration that the rtfMRI-NF data was based on healthy controls, and we anticipate greater variability in rtfMRI-NF training in the CA participants. Moreover, a sample size of 30 will allow us some room to make additional comparisons with the at-home therapy data (Aim 2) and exploratory MRI data analyses (Aim 3).

Sample size may be underpowered for the some of the proposed comparisons across aims. The amount of motor imagery necessary to improve overt tapping performance in CA patients is unknown. We modeled our power analysis parameters to target Aim 1. However, we will compare the neuroimaging data with at-home therapy performance variables (Aim 2) and will use the data from Aim 1 to conduct exploratory analyses to improve future protocols (Aim 3). The current sample size may be too small to detect significant results on all comparisons. Nevertheless, we consider the data we collect here to be highly informative for future studies and will serve as pilot data (and power analyses) for future grant applications.

Statistical methods that will be used with respect to each outcome measure:

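### The 82% power claimed for 12 participants per group at effect size .79 is 59% for the two-group test described; 82% fits only an unnamed paired or one-sample test

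*Combined protocol and SAP*

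**What the plan says.** Section 7c (Statistical plan including sample size justification) bases the sample size on three earlier studies, using G*Power. For the first, a tapping study with 17 CA participants and 17 controls, it takes a minimum group size of 12 and states that this many "participants per group yielded at least 82% power at the .05 level, one-tailed, to reject the null hypothesis of no differences between groups". The calculation is described as "based on an effect size of at least .79 (large"). It adds that, although no controls will be enrolled, "at least 12 CA participants should be sufficient to elicit RSME performance impairments". Section 3 (Background) describes the groups in that study as "matched for age, sex, and education levels".

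The second-study calculations in 7c are worded in the same way. For M1 at 1 Hz, with effect size 1.2, "a sample size of at least 13 participants per group yielded 82% power at the .05 level, two-tailed". For M1 at 4 Hz, 8 per group are said to give 84% at effect size 1.6. For further regions, with an effect of at least .78, "a sample size of 19-29 participants per group yielded at least 80% power at the .05 level, two-tailed".

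The summary in 7c says of 30 participants: "This N will be overpowered for some aspects of the study, such as tapping accuracy". The primary outcome in section 7a is the change in overt tapping accuracy within CA participants: "This will be analyzed using paired t-tests within frequency conditions".

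**The concern.** Two nearly equal effect sizes in one section lead to very different sample sizes: 12 per group at .79 and up to 29 per group at .78. The first calculation is one-tailed and the others are two-tailed, but that difference is too small to explain the gap. A reader who enters the stated inputs for the first study into a two-group test does not get 82%.

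The claim that 12 CA participants are enough rests directly on this figure. It is also the only power figure in the plan for a comparison of tapping accuracy (the third-study calculation is for a correlation), and tapping accuracy is the primary outcome. Section 7c expects the study to feed power analyses for later grant applications, so a figure that cannot be reproduced could be carried forward.

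**Working it through.** **Inputs (section 7c, first study).** n = 12 per group, standardised effect .79, α = .05 one-tailed, null of no group difference, stated power at least 82%. All power values below use the noncentral t distribution. The test family is not stated, so both candidates are computed.

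**1. Reproducing the stated figure.** Matched-pairs or one-sample t-test: df = n − 1 = 11, noncentrality = .79 × √12 = 2.737, critical t = 1.796. Power = **82.07%**. With n = 11 it is 78.6%, so 12 is also the smallest n reaching 82%. This agrees with the plan exactly.

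**2. The test as worded.** Two independent groups: df = 2n − 2 = 22, noncentrality = .79 × √(12/2) = 1.935, critical t = 1.717. Power = **59.1%**. A simulation of 200,000 trials also gave 59.1%. Rounding of .79 (.785 to .795) moves the result only between 58.6% and 59.6%.

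Other n at d = .79, independent groups:

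| n per group | Power, one-tailed .05 |
|---|---|
| 12 | 59.1% |
| 20 | 79.1% |
| 21 | 80.8% |
| 22 | 82.5% |
| 30 | 91.6% (two-tailed: 85.3%) |

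**3. Other readings of the two-group test.** At 12 per group: two-tailed 45.6%; Mann-Whitney, one-tailed, 57.3% under normality (62.7% logistic, 75.1% Laplace); α = .10 one-tailed 73.1%; α = .20 one-tailed 85.9%; .79 taken as Cohen's f 95.9%. At 17 per group, one-tailed: 72.9%. None is within two points of 82%.

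**4. The second-study figures, two-tailed .05.**

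| Effect, n per group | Stated | Independent groups | Paired |
|---|---|---|---|
| 1.2, 13 | 82% | 83.5% | 97.7% |
| 1.6, 8 | 84% | 84.5% | 97.1% |

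These follow the independent-groups test. At d = .78 that test needs 27 per group for 80% two-tailed (26 give 78.8%, 27 give 80.3%, 29 give 83.1%), in line with the plan's range of 19 to 29. Going to one-tailed lowers the need to 22 (21 give 79.9%, 22 give 81.6%), not to 12.

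**5. If the matched-pairs test was used.** The input must then be the effect size of the pair differences, dz. If .79 is a between-group d, dz = .79/√(2(1 − r)), where r is the within-pair correlation. The documents give no r, so these values are assumptions:

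| r (assumed) | dz | Power, 12 pairs, one-tailed |
|---|---|---|
| 0 | .559 | 56.7% |
| .25 | .645 | 67.3% |
| .5 | .790 | 82.1% |

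**6. What N = 30 gives the primary test.** For a paired pre/post t-test with 30 complete pairs, assuming two-sided .05, 80% power needs dz of about .53 and 90% needs about .61. The plan gives no expected dz with which to compare these.

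**The case against.** The strongest reply is that nothing was miscalculated. The exact match at 82.07%, with 12 as the smallest n to reach 82%, is what a correct run of a paired test would show, and the source study had equal groups matched on three characteristics. On this view the fault is a missing test name and loose two-group wording. That may well be right. But matching groups on age, sex and education does not establish that individuals were paired, and nothing says that .79 is a paired effect size. The cited study is not available here to settle it.

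A second reply is that the sentence pools 1 Hz and 4 Hz and gives only lower bounds, so 12 may belong to a larger effect. For 82% with 12 per group, d would have to be about 1.08. The sentence would still be wrong for an effect of .79.

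A third is that little follows: no controls are enrolled, the test will not be run, and 30 exceeds 22. This stands, and it limits the weight of the point.

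Last, missing power for the pre/post test is a separate matter, and 7c partly discloses it by calling its analyses extrapolated and warning that some comparisons may be underpowered. It is separate, but it bears on how the tapping figure may be used.

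**Conclusion.** The concern holds. For the test the sentence describes, power at 12 per group is 59%, which is 23 points below the stated 82%; 21 to 22 per group are needed for 81% to 82%. Among the standard tests tried, only a paired or one-sample test gives the stated figure, and the plan does not say that one was used. Which explanation is right cannot be decided from the documents. That the sentence does not reproduce as written is certain.

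The conclusion that 12 CA participants suffice is unsupported as it stands. N = 30 is unaffected, and the remark about being overpowered for tapping accuracy is not refuted if it means the CA-versus-control deficit (91.6% one-tailed or 85.3% two-tailed at 30 per group, d = .79). It should not be read as covering the paired pre/post primary test, for which the plan gives neither an effect size nor a power.

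**What to change.** In section 7c, first study:

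- Name the test and say whether .79 is a between-group d or a paired dz.
- If independent groups were meant, state that 12 per group give 59% power at d = .79, one-tailed .05, and that 21 to 22 per group are needed for 80% to 82%.
- If controls were individually matched and .79 is a paired effect size, say so, and describe the sample as 12 matched pairs instead of 12 in each of two groups.
- Remove or requalify the statement that 12 CA participants are sufficient.

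In the summary of 7c, keep the remark about being overpowered but limit it to detecting the CA-versus-control tapping deficit, and state that no power was calculated for the pre/post paired analysis.

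The cost is wording in two sentences of the first-study text and one of the summary. N, enrolment and the planned analyses do not change.

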Aim 1: Use rtfMRI-NF and motor imagery to train CA participants to improve motor accuracy.

- Aim 1.1: Train CA participants (N=30) to engage neural regions during motor imagery that are associated with overt finger tapping at slow (1 Hz) and fast (4 Hz) speeds.
- *Aim 1.2:* Correlate motor imagery skill (i.e., slider bar distance from target) with overt tapping performance.

• *Aim 1.3:* Evaluate the relations between overt tapping accuracy and neurological symptoms as well as motor imagery skill with offline assessments of motor imagery ability.

Aim 1 will use rtfMRI-NF during motor imagery to train CA participants to improve motor accuracy. Thirty CA participants will receive NF during motor imagery in an experiment in which we hypothesize that 1) CA participants will be able to control a NF interface; 2) imagery skill will be positively correlated to improvements in overt tapping accuracy; and 3) overt tapping accuracy will correlate with neurological signs, whereas motor imagery skill will correlate with assessed motor imagery ability.

Aim 2: Translate rtfMRI-NF learning into at-home therapy strategies for continued training.

- Aim 2.1: Examine whether motor imagery strategies from rtfMRI-NF training translate into successful at-home therapy training
- *Aim 2.2:* Compare motor imagery performance during rtfMRI NF with at-home motor imagery benefits.

Aim 2 will translate rtfMRI-NF learning into at-home therapy strategies for three weeks of continued training in which we hypothesize that 1) continued practice with imagery strategies will lead to additional improvements in motor timing and precision, and 2) performance during rtfMRI-NF training will positively correlate with at-home motor imagery performance.

Exploratory

Aim 3: Design next-generation approaches to rtfMRI-NF. The data from Aim 1 will be analyzed to optimize the future rtfMRI experiments in the CA population. We will examine whether the NF session can be streamlined to deliver more accurate NF in shorter sessions. To enable future studies to operate within an experimental medicine frame work we will examine three major questions. Aim 3.1 Are there group differences in CA versus healthy controls? Aim 3.2 Are healthy models of motor imagery viable for CA participant NF? Aim 3.3 Can the NF session be streamlined to deliver more accurate NF in more efficient sessions?

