Figure 1. Finger tapping speed and accuracy in CA. Top row: The CA group showed impaired accuracy at 1, 2 (trend), 3, and 4 Hz. Bottom row: The CA group tapped too fast at 1 Hz and too slow at 4 Hz. Yellow= group means. Error bars denote standard error [1].

slider bar that moved to the left as participants tapped too slow and to the right as they tapped too fast. We anticipated that CA participants would be able to use the external cues of the slider bar to correct tapping errors in real time, rather than rely on internal models of timing intervals.

Tapping accuracy, measured by root-mean-squared error (RSME) relative to target, was impaired at all tapping rates. Relative to controls, the CA group's tapping speed was too slow at 4 Hz, and too fast at 1 Hz. Tapping too fast at 1 Hz suggest an inability to control movements to slow down. Over/undershoot corrections in finger movements likely averaged out and masked group differences in speed 2 and 3 Hz, but were revealed in the slow (1 Hz) and fast (4 Hz) conditions. In CA, higher symptom severity, as measured by the International Cooperative Rating Scale (ICARS), was associated with slower tapping and greater error magnitude. Together, these results suggested that accuracy and speed are dissociable measures, with accuracy being the more sensitive measure of motor impairment in CA. Moreover, the 1 and 4 Hz conditions represented especially interesting tapping rates to study given the contrasting behaviors at each speed. We conducted a follow-up study to explore whether the feedback from the slider bar improved or degraded tapping behavior. We found that both groups slowed their tapping speed in the absence of continuous feedback, but the CA group's tapping accuracy deficits persisted. Based on the differences between 1 and 4 Hz, we speculate that 4 Hz may be close to the tapping limits of CA participants, but 1 Hz represents a trainable target for improving motor timing from paced visual feedback. Thus, this application's focus on 1 and 4 Hz builds on a foundation of preliminary data and aims to tease apart deficits in production from those of top-down feedback processing. We conducted an fMRI pilot study to identify neural activity patterns associated with right-

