function following injury can be regained through neural reorganization, but motor execution is not always possible or safe. Numerous clinical studies have indicated that motor imagery improves motor performance, especially when used as an adjuvant treatment with physical practice [11]. Yet, due to its very nature, motor imagery cannot be directly observed. This makes it difficult to assist and evaluate a patient's motor imagery process. Brain activity associated with motor imagery is, however, observable through neuroimaging. Moreover, with the recent development of technologies like real-time functional magnetic resonance imaging neurofeedback (rtfMRI-NF), motor imagery "behavior" can be displayed to both the patient and the clinician. For example, NF can be presented as a slider bar to indicate the degree to which a motor imagery strategy is working. Moreover, rtfMRI-NF may provide a quantifiable, objective marker of motor imagery performance, since the degree of NF control is proportional to the success of imagery to engage relevant brain regions.

We will combine rtfMRI-NF with imagery to facilitate motor network ("exercise") to improve function in CA. We will use support vector machines (SVMs) to extract motor imagery patterns and perform rtfMRI-NF as pioneered by LaConte [12, 13] (Figure 4). The SVM is first trained on an individual's fMRI patterns while performing a simple motor task (e.g., finger tapping in sync with a flashing visual cue). SVM is then used to provide neurofeedback during a subsequent task (e.g., motor imagery of finger tapping). Information about the brain's activity during motor imagery is relayed back to the person in the form of an "error signal" (i.e., distance from a target on a slider bar). Participants can use this neurofeedback to learn strategies for motor imagery that implicitly steer their brain towards optimal patterns of neural activity. As the participant changes their mental strategy, neurofeedback indicates whether the new strategy is working.

RtfMRI-NF is safe, can be performed even when physical movement is severely impaired, and targets the underlying neural responses directly rather than the

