2) At-home overt tapping accuracy improvements will be analyzed by comparing the mean accuracy on overt tapping between baseline and final measures at home (pre- and post- 3-week at-home therapy training) to compute a delta measure that will indicate magnitude of accuracy improvement at each frequency (1 and 4 Hz). This will be analyzed using paired t-tests within frequency conditions. As a follow-up analysis of improvement during the 3-week therapy (for training Groups 2 and 3 who perform daily overt tapping exercises), the mean accuracy of overt tapping at both frequencies will be measured for each session and compared using repeated measures ANOVAs and post-hoc t-tests as appropriate.

b. Secondary outcome variables.

1) The relation between imagery accuracy and tapping accuracy with supplemental assessments of imagery and motor symptoms will be analyzed using non-parametric correlation tests, such as Spearman's rank-order correlation coefficient test, because of the ordinal values in the KVIQ and ICARS assessments. Mean imagery accuracy and tapping accuracy scores from the final MRI assessment will be compared separately to the KVIA an ICARS.

2) The relation between brain activity during imagery NF and overt tapping improvements will be analyzed using Pearson correlations between the mean of region of interest activity (minus rest) during NF training and the RSME delta scores.

3) The influence of ancillary measures on overt tapping and motor imagery accuracy will be analyzed using non-parametric correlation tests (e.g., Spearman's rank) because of the ordinal values in the HAM-A, HAM-D, CCAS, and WRAT assessments. Mean imagery accuracy and tapping accuracy scores from the final MRI assessment will be compared separately to each of the assessments.

c. Statistical plan including sample size justification and interim data analysis.

We plan to enroll 30 participants in this study. The sample size was determined through a power analyses using G*Power 3.1.9.2 software [40]. Because motor imagery, with or without rtfMRI-NF, has never been used as a treatment approach for people with cerebellar ataxia (CA), as proposed here, our power analyses are extrapolated from information we have obtained that in three prior studies that support the premise and feasibility of Aim 1, which is to use rtfMRI-NF and motor imagery to train CA participants to improve motor accuracy.

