In general, comparisons between measures with continuous variables (e.g., accuracy) within participants will be conducted using paired-tests, repeated-measures ANOVAs, and post-hoc t-tests as appropriate. Pearson correlations will be run between continuous variables (e.g., motor imagery accuracy and delta scores). Non-parametric tests will be used when assessments that with ordinal values (ICARS, KVIQ, mood, and cognitive ancillary measures) are included.

d. Early stopping rules. N/A

8. Risks

a. Medical risks, listing all procedures, their major and minor risks and expected frequency.

Risks/Benefits

The following relevant risk/benefit considerations and potential ethical issues may arise as part of the proposed study. Any adverse events will be promptly reported to the IRB. As this is not an intervention study, participants will be informed as part of the consent process that their medical care will not be affected or altered by their decision to participate in this research. There are no financial risks to the participant.

MRI: Screening of participants will consist of checks for contraindications to MRI scanning. Urine pregnancy testing will be conducted on-site for women of child bearing age. Currently pregnant participants will be excluded. There are no known significant risks for an MRI exam. Subjects, may, however, experience mild discomfort by the noise made by the magnet during the procedure, bothered by feelings of claustrophobia, or anxiety. There is a risk that the subject may become bored or fatigued with cognitive testing while in the scanner.

EMG: The EMG will be utilized to determine whether participants are moving their finger muscles during the imagery condition in the MRI scanner, in which they are not supposed to do so. To apply the surface electrodes on the participant's arm, skin prepping gel similar to a gentle exfoliating cream will first be applied and rubbed onto the participant's skin in order to remove any dead skin. There is a risk that subjects may not like the feeling of the cream or that their skin will become slightly irritated. The risks of the electrodes are the same as those of applying a band-aid on someone's arm: subjects may be uncomfortable with the adhesive feeling of the electrodes, and the electrodes might feel similar to ripping off a band-aid when taken off.

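### Should the correlations of imagery accuracy and ROI activity with tapping improvement be adjusted for pre-NF tapping error?

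*Combined protocol and SAP*

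**What the plan says.** Section 7a item 1 defines improvement by "comparing the mean accuracy on overt tapping between baseline and final measures (pre- and post- NF) to compute a delta", separately at 1 and 4 Hz. Two correlations use that delta:

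- **Imagery accuracy.** Section 7c, in its general statement of methods: "Pearson correlations will be run between continuous variables (e.g., motor imagery accuracy and delta scores"). This serves Aim 1 hypothesis 2 in section 2, that "imagery skill will be positively correlated to improvements in overt tapping accuracy". Aim 1.2 words the objective more loosely: "Correlate motor imagery skill (i.e., slider bar distance from target) with overt tapping performance", with no time point.
- **ROI activity.** Section 7b item 2: "analyzed using Pearson correlations between the mean of region of interest activity (minus rest) during NF training and the RSME delta scores". This is the correlation for which section 7c gives a sample size (17 to 22 participants, at least 81% power, one-tailed 5%).

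Section 7 names no regression on baseline, partial correlation, or correlation of either predictor with pre-NF error. The nearest planned analysis is section 7b item 1: "Mean imagery accuracy and tapping accuracy scores from the final MRI assessment will be compared separately to the KVIA an ICARS".

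**The concern.** When a change score is correlated with a measured characteristic, any relation between that characteristic and the baseline enters the result. This design offers two possible routes.

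- **Run-specific route.** According to the Background, the feedback classifier is first trained on the individual's "fMRI patterns while performing a simple motor task (e.g., finger tapping in sync with a flashing visual cue"). On the section 4a schedule only one tapping run precedes imagery, so that run apparently supplies both the classifier's training data and the pre-NF half of delta. If poor tapping in that run also lowered the imagery score, the raw correlation would be pulled away from hypothesis 2 and a true effect could be masked.
- **Severity route.** The Background reports that higher ICARS severity "was associated with slower tapping and greater error magnitude". Severity might also affect imagery or ROI activity.

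At stake are the test of hypothesis 2 and the ROI correlation. Section 7c also says the data will feed power analyses for later grant applications, so a distorted correlation could carry forward.

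**Working it through.** **Inputs.** From the documents: N=30, the definition of delta, and the section 7c figures for the ROI correlation. Not in the documents, so assumed: the correlation g of a predictor with pre-NF error (0, or 0.3 to 0.5 in size) and the pre-post correlation of tapping error, rho (0.5 to 0.8). Improvement is pre minus post error. The imagery score is signed so that higher is better; distance from target, as in Aim 1.2, would reverse the signs.

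**1. The plan's own figure.** The pilot correlation is not printed, so it can only be back-solved. By Fisher z, r = tanh[(1.645 + 0.878)/√(N−3)]. N=22 gives tanh(2.523/4.359) = 0.52, and N=17 gives tanh(2.523/3.742) = 0.59. A noncentral-t calculation gives 0.49 to 0.54. These are correlations with delta, in healthy adults.

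**2. Expected raw correlation when there is no effect.**

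- *Run-specific route* (the predictor depends on observed pre-NF error; equal SDs): corr(x, delta) = g√((1−rho)/2). With rho=0.5 and g=±0.3 this is ±0.3 × 0.5 = ±0.15; with g=±0.5 it is ±0.25. The two-sided critical value at N=30 is 0.361, so the shift is not trivial. At rho=0.5, one-tailed rejection in favour of hypothesis 2 is 0.8% and 0.2% for g=−0.3 and −0.5, and 20% and 38% for g=+0.3 and +0.5.
- *Stable-severity route* (pre and post are the same true level plus independent noise; the predictor depends only on the true level): cov(x, pre) = cov(x, post), so corr(x, delta) = 0 and the raw test is correct. The partial correlation with improvement is −g(1−rho)/√((1−g²)(1−rho²)). With g=−0.5 and rho=0.5 this is 0.25/0.75 = 0.33 although nothing is there.

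**3. Simulation** (N=30, 40,000 replicates, rho = 0.5, 0.7, 0.8; two-sided 5% rejection):

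| Scenario | Raw | Baseline-adjusted |
|---|---|---|
| g=0, no effect | 5% | 5% |
| g=0, partial r 0.49 | 70%-77% | 79%-80% |
| Run-specific, g −0.3 to −0.5, partial r 0.49 | 39%-66% | 80% |
| Run-specific, g −0.3 to −0.5, partial r 0.30 | 6.5%-21% | 35%-36% |
| Run-specific, g +0.3 to +0.5, partial r 0.49 | 90%-98% (partly upward bias) | 79%-80% |
| Stable severity, no effect, g of either sign | 5% | 8%-43% |
| Same, with a 30% gain in true error unrelated to imagery | 7%-21% | 7%-27%, opposite direction |

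The only sidedness the plan gives for this type of correlation is one-tailed. On that footing the masking gap narrows to 51%-77% against 87%-88%.

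**4. Would showing both results settle it?** Masking predicts a negative g, a null raw result and a positive adjusted result. A negative stable-severity link with no effect predicts the same pattern. The share of trials in which exactly one of the two 95% CIs excludes zero is:

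- 15%-42% under masking at partial r 0.49;
- 7%-44% under stable severity with no effect;
- 3%-16% at g=0, where both tests are valid.

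The observed g helps little. At N=30 an observed value of 0 has a 95% CI of ±tanh(1.96/√27) = ±0.36, which does not exclude a link of −0.3.

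**5. What the documents say about the link.** The Background states that the classifier is trained on a motor-task scan. It does not say that poor tapping degrades the imagery score. For ROI activity, the pilot scans found higher cortical recruitment in ataxia irrespective of speed and performance. That is a group-level result during tapping, and it points to a weak link if to any. The planned correlation of imagery accuracy with ICARS gives a partial look at the severity route, but covers neither run-specific error nor ROI activity.

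**The case for a change.** The strongest case for a change is that the omission is real and cheap to fill. One regression per measure and frequency, on data already collected, costs one degree of freedom. With no link the adjusted test is slightly the more powerful (79%-80% against 70%-77% at partial r 0.49). Hypothesis 2 rests on this correlation, a null result could hide a real effect, and a choice between raw and adjusted made after seeing both would be open to criticism.

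The description of the omission stands: section 7 prescribes no such check, and the ICARS correlation replaces it only in part. The two-way bias is also arithmetically correct if a run-specific link exists. With a positive link and a 30% gain in true error unrelated to imagery, even the stable-severity route gives one-tailed false support in 12%-32% of trials under the raw test.

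It does not stand that the addition would tell a null result from masking, because the same pattern of results arises where the raw test is right. A rule triggered when only one CI excludes zero compares two significance statuses rather than testing a difference, and it can fire when neither analysis is at fault. Masking also presupposes that the target is the effect given baseline, whereas hypothesis 2 speaks of correlation with improvement. As the raw correlation is the only one named, it remains the planned test, and anything adjusted would be read as supplementary.

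**Conclusion.** No change is needed. The planned Pearson correlation matches the stated hypothesis, and neither analysis is right in all cases. The raw one fails if a predictor is tied to run-specific baseline error, or is tied to severity while gain depends on true baseline error. The adjusted one fails if the tie runs only through stable severity. Choosing the raw correlation is a fair trade-off, and a paired sensitivity analysis would gain little at N=30.

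The possible cost is limited: power of 39%-66% instead of about 80% at partial r 0.49 in the masking case, and none at zero link. All these figures rest on assumed values of g and rho and on linear models with normal errors. The primary paired t-tests are unaffected, and section 7c already concedes limited power and describes the data as pilot data. Because pre-NF error is recorded, an analyst who wishes to can report each predictor's correlation with it, and the baseline-adjusted estimate, with 95% CIs as description. Evidence of a link to run-specific error in the baseline would be a reason to look at this again; the documents contain none.
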